2.1 Objectives & Hypotheses

Hypotheses:

- A. After routine care and reversal of neuromuscular block as per usual clinical routine, and after tracheal extubation, surgical patients randomized to receive sugammadex vs. placebo in the OR will:
 - 1) have a lower incidence of "Decreased MV" [MV <80% MV predicted (MV_{PRED}) based on BSA] as well as lower average MV sustained at 15-30 minutes after PACU arrival than placebo patients
 - 2) have a lower incidence of "Low MV" as well as lower average MV at PACU discharge. An instance of "low MV" occurs when the measured MV is <40% MV predicted (MVPRED) based on BSA, for any contiguous 10 minutes in the 30 minutes leading up to PACU discharge.
- B. A smaller fraction of patients in the sugammadex group than in the placebo group spend more than 2 minutes in the PACU with a sustained "Low MV."
- C. A smaller fraction of patients in the sugammadex group than in the placebo group spend more than 2 minutes in the PACU with a sustained "Low MV" when corrected for PACU length-of-stay (LOS).
- D. The average %MV predicted is greater in the sugammadex group than in the placebo group.
- E. PACU LOS is shorter in patients receiving sugammadex as compared with placebo patients.
- F. Fewer patients in the sugammadex group have respiratory complications or require respiratory monitoring (O₂ desaturation, atelectasis, O₂ administration, CPAP, BiPAP, reversal medication).

	
 G. The sugammadex group has higher train-of-four (TOF) ratios than the placebo group at equivalent time points throughout their PACU stay. H. The ExSpiron is able to identify respiratory depression (defined as instances of MV <40% MV_{PRED} lasting at least 1 minute) occur prior to instances of SpO₂ <90% lasting at least 2 minutes). I. Lower MV measurements (corrected for total morphine equivalents administered) are correlated with lower TOF ratios.
--	--

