	
patients will be informed about the study and the study will be explained to them. They will be able to ask questions. If they would like to participate, written informed consent will be obtained. Recruitment at Mayo Clinic site will be conducted by Investigators on the day of surgery. Patients will be identified and approached before they are taken to the preoperative area. A private room located near the surgical area will be used for consenting of prospective participants. Family and/or friends will be allowed to remain with a patient during the consenting process. Patients usually arrive approximately 2 hours prior to their scheduled surgery time, which will be adequate time to discuss the study and allow patients to make an informed decision whether or not to participate in this research study.
 
2) Randomization:
 
Patients will be randomized to one of two groups: administration of sugammadex (n=150) vs. placebo (n=150) prior to tracheal extubation in the OR.
 
3) Prior to Procedure (in the OR or preoperative area):
 
 i. For RVM monitoring, ExSpiron PadSet will be placed on the patient's thorax (see Appendix A for placement instructions). Deviations from standard placement will be documented. Once in the OR the ExSpiron will be connected and the ExSpiron will be synchronized to the ventilator. ii. For TOF monitoring, skin ECG electrodes will be placed along the ulnar nerve on the volar forearm, as per routine clinical protocol. Visual or tactile intraoperative monitoring of neuromuscular block level will be performed according to the clinicians' usual routine. At the end of surgery, once the clinician has determined that recovery of neuromuscular block is adequate (after administration of standard of care reversal agents) for maintenance of spontaneous ventilation, the TOF will be determined objectively (it will be measured with the currently available monitor, TOF-Watch or StimPod), and then the patient's trachea will be extubated, as per usual clinical routine. In 150 of the 300 patients, a dose of sugammadex (2 mg/kg) will be administered, and then routine TOF measurements will be made in the PACU. 
4) Operating Room (OR):
 
 a. Record all medications (dose, route, time)
--	--

- b. Record surgery start and end times
- c. Record position changes
- d. Record intubation and extubation times

5) Recovery Room (PACU):

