2.7 Statistical Analysis and Sample Size Justification**A. Blinded Data Analysis:**

The investigator will be responsible for overall analysis of the data with assistance from Respiratory Motion staff in analysis of RVM data. The study will be double blinded with no knowledge of drug vs. placebo administration by investigator, clinical care providers or researchers performing the primary data analysis. A patient can be unblinded on an urgent basis if it is deemed necessary for the clinical care of the patient.

Study medication (sugammadex and placebo) will be prepared by the institutional pharmacy, and will be dispensed to the investigative team member according to the patient group assignment. The site study coordinator will call the pharmacy and alert them once a patient is enrolled in the study. The drug (sugammadex or placebo) will be prepared by the Pharmacy personnel according to the randomization sequence. The clinician administering the drug (sugammadex or placebo) will be blinded to the drug identity.

The investigators will be responsible for analyzing the study data, and the analysts will be blinded to patients' group assignment during the execution of the study. For the purpose of the final analysis, the official clinical database will not be unblinded until medical/scientific review has been completed and the investigators have been assured that the data are complete.

B. Statistical Analysis:

- a. Using Fisher exact test, we will compare across the two groups the incidence of:
 - i. Sustained MV<80%MV_{PRED} for at least 1 minute in the first 15-30 minutes after arrival in PACU
 - ii. Sustained MV<40% MV_{PRED} for more than 10 contiguous minutes of the last 30 minutes prior to PACU discharge
 - iii.. Sustained MV<40%MV_{PRED} for at least 2 minutes after opioid administration (amongst patients receiving opioids in the PACU)
 - iv. Sustained MV<40%MV_{PRED} for at least 2 minutes in the absence of opioids (amongst patients w/o opioids in the PACU)
 - v. Sustained MV<40%MV_{PRED} for at least 2 minutes after opioid administration (amongst patients receiving opioids in the PACU) when corrected for PACU LOS
 - vi. Sustained MV<40%MV_{PRED} for at least 2 minutes in the absence of opioids (amongst patients w/o opioids in the PACU when corrected for PACU LOS
 - vii. Adverse events, including:
 - 1. Respiratory complications (O₂ desaturation, atelectasis, respiratory status requiring advanced monitoring, etc.)

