	
c. Using paired t-tests we will compare:
 
 i. MV, TV, and RR measurements before and after sugammadex administration 
d. We will perform sensitivity and specificity analysis to evaluate the ability of sugammadex to:
 
 i. Decrease respiratory complications (O_2 desaturation, atelectasis, respiratory status requiring advanced monitoring, etc.) ii. Decrease the need for respiratory interventions (O_2 administration, CPAP, BiPAP, medications, etc.) iii. Decrease transfers to step-down or ICU iv. Decrease LOS in PACU v. Increase MV in the PACU at the following time points: 
 1. On arrival 2. After opioids 3. At discharge 
e. We will perform multi-factor Analysis of Variance (MFANOVA) with dependent variables: "sustained MV<40% MV_{PRED} for at least 2 minutes", "Adverse event", PACU LOS, etc... as defined in each hypothesis, based on demographics to demonstrate group uniformity.
 
f. We will use Pearson correlations and linear regressions, without regard to treatment group to compare:
 
 i. MV measurements and TOF ratios ii. MV measurements and total opioid dose iii. Pain scores and total opioid dose iv. MV measurements and pain scores 
C. Multiplicity: For the purposes of this work, we will treat Hypothesis A1 as a primary objective and A2 as a key secondary. We will consider $p<0.05$ to be statistically significant for the primary objective and this result will be the main outcome of our study. We will test the key secondary objective (at $p<0.05$ significance level) only if we have achieved significance with the primary.
 
We will continue with testing the remaining secondary hypotheses only if we have significant results from the primary and the key secondary. For each additional secondary hypothesis, we will calculate statistical significance both with and without Hochberg correction.¹⁴ If we discover marginally significant effects in any of the remaining hypotheses, we will propose additional studies powered and geared towards specifically addressing said hypotheses.

--	--

D. Power/Sample Size:

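### The multi-factor ANOVA in Section 2.7 B.e models outcomes, so it cannot show that the arms are alike at baseline, and it suits the two yes/no outcomes poorly

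*Combined protocol and SAP*

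**What the plan says.** Item e of Section 2.7 B announces a "multi-factor Analysis of Variance (MFANOVA) with dependent variables" that are trial outcomes. Three are named: sustained MV below 40% of predicted for at least 2 minutes, adverse event, and LOS. The list is then left open: "PACU LOS, etc... as defined in each hypothesis". The analysis is described as "based on demographics to demonstrate group uniformity". The demographic factors are not listed. Treatment arm is not named as a factor, and it is not excluded either.

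Two of the three named outcomes are yes/no for each patient. Hypothesis B in Section 2.1, which concerns low MV, is worded as a fraction: "A smaller fraction of patients in the sugammadex group than in the placebo group spend more than 2 minutes in the PACU with a sustained". Item a of Section 2.7 B treats low MV and adverse events as incidences: "Using Fisher exact test, we will compare across the two groups the incidence of". LOS is continuous and is compared by a two-sample t-test in item b.

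Section 2.9 says that demographics, height, weight and pulmonary history will be collected. Section 2.7 plans no summary of them by arm and no regression model for yes/no outcomes.

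**The concern.** Item e is the only place in Section 2.7 that speaks to whether the groups are comparable, and it addresses the question with the outcome on the left-hand side of the model. Whatever the ANOVA shows about demographics and outcome, a report that relied on it to say the groups were uniform would be making an unsupported statement. A factor that is not significant would not demonstrate uniformity in any case.

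The second matter is the fit of the model. ANOVA assumes a constant residual variance and an unbounded mean. A yes/no outcome has variance p(1−p), which changes with the risk p, and its mean must lie between 0 and 1. The analysis would also produce no odds ratio or risk ratio for the two yes/no outcomes.

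**Working it through.** The plan states no figure for item e, so there is nothing to reproduce. The check has two parts. Both use 300 patients, from "administration of sugammadex (n=150) vs. placebo (n=150) prior to tracheal extubation in the OR". The factors, their effects and the size of the imbalance are assumptions, because the documents give none.

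**Part 1: does the model respond to imbalance between arms?** Assume one two-level demographic factor, an overall event rate of 16.5%, and no effect of arm. A 0/1 outcome is fitted by least squares on the factor and arm, so the reading with arm in the model is the one tested. Imbalance, where present, is 65% against 35%. A factor effect, where present, is 15 points: 16.5% − 7.5% = 9% against 16.5% + 7.5% = 24%. As a yardstick only, the factor is also compared directly between arms. Each row is 4,000 simulated trials; the entries are the share with p < 0.05.

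| Arms imbalanced? | Factor affects outcome? | Outcome ANOVA: factor | Outcome ANOVA: arm | Direct comparison by arm |
|---|---|---|---|---|
| No | No | 5.3% | 5.2% | 5.5% |
| No | Yes | 95.0% | 4.5% | 5.4% |
| Yes | No | 5.0% | 5.0% | 99.9% |
| Yes | Yes | 93.2% | 4.9% | 100% |

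The factor column follows the effect on outcome and hardly moves with imbalance (5.3% against 5.0%; 95.0% against 93.2%). The arm column does not respond to imbalance either. Only the direct comparison does.

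**Part 2: how badly does ANOVA behave on a yes/no outcome?** With the assumed risks of 9% and 24% across the factor, the variances are 0.09 × 0.91 = 0.082 and 0.24 × 0.76 = 0.182, so they are unequal whenever the factor matters. To look at the test itself, a main-effects ANOVA on sex, three age groups, site and arm was simulated 5,000 times per event rate, with no true effects.

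| Event rate | F test rejects at 5%: arm | F test rejects at 5%: sex | Trials with a fitted risk below 0 |
|---|---|---|---|
| 22% | 4.8% | 5.2% | 0.1% |
| 16.5% | 5.3% | 5.6% | 1.3% |
| 5% | 4.7% | 5.2% | 44.3% |
| 2% | 4.5% | 4.7% | 84.9% |
| 1% | 2.6% | 2.4% | 91.1% |

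Type I error runs from 4.5% to 5.6% down to a 2% event rate and is conservative at 1%. Impossible fitted risks are rare at 16.5% and above and common at 5% and below. That last result is for a main-effects model. A fully crossed ANOVA fits cell proportions, which cannot fall below 0, and item e does not say which is meant.

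**The case against.** The strongest defence is that item e is underspecified rather than mistaken. Hypotheses A to G all compare sugammadex with placebo, item e refers to those hypotheses, and the next item (f) is expressly done ignoring treatment group, a qualifier that item e lacks. Arm plus demographics is therefore a plausible reading, close to a covariate-adjusted analysis. The uniformity phrase could also mean a consistent treatment effect across demographic groups. This stands in part: a reader might infer that arm is left out of the model, but the documents do not establish that. It does not rescue the stated purpose. With arm included, the model gives an adjusted arm effect on outcome and still no baseline comparison. Consistency of effect would need arm-by-demographic interactions, which are not specified, and non-significant interactions would not demonstrate it.

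A reader might also use the 22% and 11% rates in Section 2.7 D to quantify unequal variance between arms. Those rates are for low MV at PACU discharge, defined over 10 contiguous minutes. Item e concerns the 2-minute outcome, for which no rate by arm is given, and a between-arm contrast bears on the model mainly if arm is in it.

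Nor do the calculations support calling the F test invalid, since its type I error is near nominal unless events are very rare. The yes/no objection does not reach LOS, which is continuous.

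Finally, item e carries no decision rule, and no main conclusion rests on it. The yes/no endpoints are compared by Fisher exact test, LOS by t-test, and the testing order in Section 2.7 C runs from A1 to A2 before anything else.

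**Conclusion.** The point holds in limited form. The conclusion that item e sets out to reach cannot follow from a model of outcomes, whether or not arm is a factor. This rests on what the model compares and not on the simulation, which only illustrates it under assumed factors, effects and imbalance. It applies to all three named outcomes.

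The mismatch with yes/no outcomes is the lesser matter and applies to two of the three. It costs interpretability (unequal variances, possible impossible fitted risks, no ratio measure) more than it costs error control.

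A reader might infer that the trial's efficacy conclusions are at risk. They are not: the primary and key secondary tests are unaffected. This is a low-priority correction to a supporting analysis.

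**What to change.** Three changes to Section 2.7 B:

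1. Delete the phrase about demonstrating uniformity from item e.
2. Add a baseline table that summarises the demographics already collected, by arm, descriptively and without significance tests.
3. Recast item e as a supportive covariate-adjusted analysis. Name treatment arm and a short covariate list fixed in advance (for example site and age), and replace the open-ended list of outcomes with a closed one. Use logistic or another binomial regression for yes/no outcomes with enough events, and report the adjusted arm effect with its confidence interval. Use a linear model for LOS. State beforehand how sparse outcomes are recognised, and keep the Fisher exact test alone for those.

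The sparse-event provision matters. Section 2.2 puts critical respiratory events at 0.8%, and even applied to all patients that is 0.008 × 300 = 2.4 events, too few for a multi-term regression.

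The choice of covariates and the scale for LOS are for the investigators; the documents give no LOS distribution that would settle the latter. The cost is SAP wording and slightly more programming, with no change to data collection or sample size.

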2.5 Study Procedures

	
which may decrease the incidence of residual neuromuscular block.)
 
 1) The ExSpirom will be placed on the patients' chest prior to extubation. ExSpirom data will be collected starting prior to tracheal extubation, during transport from OR to PACU, and in PACU. 2) Patient care staff will be blinded to the ExSpirom numerical and trending data for MV, TV and RR, but the respiratory trace will be displayed to demonstrate that the ExSpirom is functioning. Of note, the gain on the trace is variable so the size of the breath visualized on the screen is not correlated to the volume of the breath. This will maintain blinding of the patient care staff. 3) TOF Monitoring with an objective monitor (TOF-Watch or StimPod) will be used in all patients once the decision to extubate the patients' trachea is made. The monitoring will continue in the PACU until full recovery (TOF=1.0) is documented. Monitoring will be performed as per usual clinical routine via surface ECG electrodes. In the PACU, the current amplitude will be decreased to 30-40 mA, current intensities that are used routinely for patient care in other centers and that do not result in patient discomfort. 4) Patient care staff will be blinded to TOF data. Only the investigator assigned to the PACU data retrieval will know the results of TOF Monitoring. 5) Patient care should follow standard hospital protocol. 6) Physiologic monitoring and clinical assessment data will be recorded as per standard protocol in the PACU. 7) All other therapies and medications including oxygen, CPAP, opioids and sedatives will be delivered in accordance with standard of care. 8) Doses and times of all medications (such as opioids, sedatives, etc.) or respiratory interventions (such as albuterol, respiratory treatment, suctioning, high flow oxygen, CPAP, BiPAP, etc.) will be recorded throughout the entire perioperative period (pre-op, OR, PACU). 9) Pain scores based on a standard analog scale (1-10) will be recorded. These will be obtained per standard clinical practice. 10) Arterial or venous blood gas values and Chest x-rays taken in the OR or PACU will be recorded when obtained as part of standard care. 
B. Study Procedures
 
 1) Screening and Recruitment: Study personnel will review the surgery schedule to identify appropriate and eligible patients. Eligible
--	--

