 - 2. Respiratory interventions (O₂ administration, CPAP, BiPAP, medications, etc.)
 - 3. ICU or step-down unit transfer
 - viii. Normal TOF ratio (>0.90) at equivalent time points in the PACU (e.g. on arrival, at discharge, etc...)
- b. Using 2-sample t-tests we will compare:
 - i. Average MV during the 15-30 minutes after arrival at the PACU
 - ii. Average MV during the 30 minutes prior to the time cleared for PACU discharge
 - iii. Average LOS in the PACU
 - iv. Average pain scores
 - v. Average total opioid dose (morphine equivalents) in the PACU

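### Section 2.7 B.f tests MV against TOF and total opioid dose without saying how repeated readings within a patient are handled or limiting the opioid total to doses given before the MV reading

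*Combined protocol and SAP*

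**What the plan says.** Section 2.7 B.f states: "We will use Pearson correlations and linear regressions, without regard to treatment group to compare". The first two pairs are "MV measurements and TOF ratios" (f.i) and "MV measurements and total opioid dose" (f.ii). Item f does not name a reading, a time window, a per-patient summary or a period for the opioid total.

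The analysis of f.i serves Hypothesis I in section 2.1: "Lower MV measurements (corrected for total morphine equivalents administered) are correlated with lower TOF ratios".

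The data are repeated within patient:

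- **MV.** Section 2.5, A item 1: "ExSpirom data will be collected starting prior to tracheal extubation, during transport from OR to PACU, and in PACU".
- **TOF.** Section 2.5, A item 3: "The monitoring will continue in the PACU until full recovery (TOF=1.0) is documented". Section 2.7 B.a.viii gives arrival and discharge as examples of comparison times and leaves the list open.

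The nearest definition of the opioid variable belongs to another analysis, the t-test in section 2.7 B.b.v: "Average total opioid dose (morphine equivalents) in the PACU". Section 2.5 (A item 8, and the OR and PACU recording lists) requires the time of every dose to be recorded.

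**The concern.** The usual p-values and confidence intervals for Pearson correlation and ordinary regression assume independent observations. Several MV–TOF pairs from one patient are not independent. If they are entered as separate observations, intervals are too narrow and the false-positive rate exceeds 5%. Because TOF monitoring ends at full recovery, the number of pairs would also differ between patients.

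The opioid variable raises a second question. A total that runs past the MV reading includes doses that cannot have influenced that reading. An association with such a total mixes any effect of opioids on breathing with later prescribing, which may itself follow pain.

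At stake are Hypothesis I and part of the evidence for secondary objective (b), which asks whether respiratory depression comes from opioids or from residual block. While the unit of analysis and the dose window stay open, both can be chosen after the results are seen.

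**Working it through.** The plan gives no power, sample size or expected correlation for item f, so there is no figure of its own to reproduce. The check shows what each possible reading of f would imply.

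**1. Repeated readings**

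Inputs: 300 patients (section 2.7 D). The number of pairs per patient, m, and the within-patient correlations are not in the documents, so ranges are assumed.

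With no true association and readings pooled as independent, the variance of the estimate is inflated by

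D = 1 + (m − 1) × ICC_MV × ICC_TOF,

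and a nominal two-sided 5% test has actual error 2 × [1 − Φ(1.96/√D)].

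Worked case, m = 3 and both correlations 0.6: D = 1 + 2 × 0.36 = 1.72; 1.96/√1.72 = 1.49; error = 0.135.

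| m | Correlation (both) | D | Error, formula | Error, simulation |
|---|---|---|---|---|
| 3 | 0.4 | 1.32 | 0.088 | 0.089 |
| 3 | 0.6 | 1.72 | 0.135 | 0.123 |
| 3 | 0.8 | 2.28 | 0.194 | 0.193 |
| 5 | 0.4 | 1.64 | 0.126 | 0.116 |
| 5 | 0.6 | 2.44 | 0.210 | 0.225 |
| 5 | 0.8 | 3.56 | 0.299 | 0.303 |

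The simulation used 300 patients, equal m for all, and 1,500 runs per cell. Formula and simulation agree within simulation error.

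For f.ii, a per-patient opioid total is constant within patient, so its correlation is 1. With MV correlation 0.5:

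- m = 3: D = 1 + 2 × 0.5 = 2.0, error 0.166.
- m = 5: D = 1 + 4 × 0.5 = 3.0, error 0.258.

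With one value of each variable per patient, a separate simulation (300 patients, 3,000 runs) gave errors of 0.047 to 0.055, which is the nominal level.

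**2. Timing of the opioid dose**

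Section 2.1 (Hypothesis I), 2.7 B.b.v and 2.7 B.f.ii all use a total, and none limits it to doses before the MV reading. Set against MV at 15–30 minutes after arrival, a PACU total can include doses given later. Set against MV in the 30 minutes before discharge clearance, it would probably include few.

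To see what later doses can do, 300 patients were simulated (500 runs per case). Each unit of prior dose truly lowers MV by 0.3. Pain may raise MV (coefficient g) and may raise dosing (coefficient h for later doses, 0.3h for prior doses). All coefficients are assumptions.

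| g | h | Correlation of MV with total | Correlation of MV with prior dose |
|---|---|---|---|
| 0 | 0 | −0.128 | −0.189 |
| 0 | 0.5 | −0.132 | −0.193 |
| 0.3 | 0.5 | +0.029 | −0.129 |
| 0.5 | 0.7 | +0.176 | −0.059 |
| 0.7 | 0.7 | +0.274 | −0.009 |

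When pain does not affect MV, the total only weakens the correlation. When pain drives both MV and dosing, the total turns it positive although the opioid lowers MV. Prior dose kept the correct sign in these cases but was pulled towards zero, so pain still confounds it.

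**The case against.** The strongest reply is that the plan never says readings will be pooled. The continuous comparisons in section 2.7 B.b use patient-level summaries: average MV in two windows, average pain score and total opioid dose. A total dose pairs naturally with one MV summary per patient, and on that reading the inflation vanishes. This stands. A reader might infer that the plan treats repeated readings as independent, but the documents do not state it. What remains is that f refers to neither window and offers no rule for choosing among several TOF readings.

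Three other stronger readings are also unsupported:

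- **That the direction of the MV–TOF association is unreliable.** Ignoring clustering distorts standard errors; it does not by itself reverse a sign. The sign problem concerns MV–opioid only, and in the simulation it arose only where pain affected both MV and dosing. Staff are blinded to numerical MV, which limits dosing in response to MV but not in response to pain.
- **That slow-recovering patients weight the analysis by its outcome.** With MV regressed on TOF, TOF is the predictor. Extra readings at low TOF do not in themselves bias the slope, and the simulation held the number of pairs equal.
- **That objective (b) depends on these correlations alone.** Items B.a.iii–vi and B.b.iv–v also serve it, and a.iii and a.v already look at MV after opioid administration.

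It is also fair that the consequences are limited. Hypothesis I is tested only after A1 and A2 both succeed, significance is reported with and without Hochberg correction, and marginal effects lead to further studies. Hochberg correction does not, however, repair a p-value that is invalid to begin with.

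**Conclusion.** The point holds as a gap in specification. Section 2.7 B.f names methods that assume independent observations for data that are repeated within patient, and it gives no within-patient method or single-pair rule. Valid p-values therefore cannot be assured. If readings are pooled, actual error is about 9–19% with 3 pairs per patient and 12–30% with 5, on assumed within-patient correlations of 0.4–0.8. If one pair per patient is used, there is no inflation.

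The dose window is a separate gap that a single pair per patient would not close. Because the total may include doses given after an early PACU reading, the MV–opioid association cannot be read as an opioid effect. A reversed sign is possible, not established; it depends on pain driving both MV and dosing.

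The effect is confined to Hypothesis I and the supporting associations in f. A1, A2 and the sample size do not depend on them.

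**What to change.** In section 2.7 B.f.i and f.ii:

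1. **Unit of analysis.** Model MV as a percentage of predicted on time-matched TOF, using a linear mixed model with a patient random intercept and a term for time since PACU arrival. Cluster-robust standard errors are an alternative. If a simple correlation is preferred, name one MV–TOF pair per patient in advance, for example at PACU arrival.
2. **Opioid variable.** Replace the total dose with cumulative morphine equivalents given up to the MV reading, derived from the recorded dose times.
3. **Interpretation.** State that the MV–opioid result remains an association, because confounding by pain is not removed by timing the dose.

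The cost is SAP wording and modest programming on data already being collected. If the intention was to pool readings, intervals will be wider than the unadjusted ones.

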Randomized Double---Blinded, Controlled
Trial to Compare the Effectiveness of
Sugammadex vs. Placebo to Prevent
Residual Neuromuscular Block in the Post---
Anesthesia Care Unit as Evaluated with a
Non---Invasive Respiratory Volume Monitor

NCT02728726

6/29/2017

f

Merck Investigator Studies Program (MISP) Protocol Template

Requirements for Submitting a Full Proposal

Section #1 - MISP Protocol Identification

Study Title:	Randomized Double-Blinded, Controlled Trial to Compare the Effectiveness of Sugammadex vs. Placebo to Prevent Residual Neuromuscular Block in the Post-Anesthesia Care Unit as Evaluated with a Non-Invasive Respiratory Volume Monitor
Request Date:	Protocol Version date 6/29/17
Institution Name:	Mayo Clinic, Jacksonville University of Texas - UT Health, Houston
Investigator Contact Information:	J. [name] Assistant Professor of Anesthesiology Department of Anesthesiology Mayo Clinic [name] O: [contact] E: [contact] [name] The University of Texas, UTHealth Department of Anesthesiology [name] [REDACTED] [REDACTED]

Section #2- Core Protocol

The Primary objective of this study is to determine whether patients who receive sugammadex immediately after tracheal extubation will exhibit a decrease in the incidence of postoperative residual paralysis and an associated decrease in the incidence of postoperative respiratory depression (which can precede critical respiratory events, CRE).

The Secondary objectives are to: a) determine whether patients receiving sugammadex will have a normal TOF ratio (>0.90) indicative of full neuromuscular recovery in the PACU; and b) to improve patient safety by documenting whether postoperative respiratory depression (decreased MV below 80% and 40% of predicted MV as assessed by a Respiratory Volume Monitor) is due to opioid administration vs. postoperative residual neuromuscular block (by comparing postoperative VAS scores and total opioid administered).

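### Hypothesis I asks for an MV–TOF association corrected for opioid dose, but no planned analysis contains MV, TOF ratio and opioid dose together

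*Combined protocol and SAP*

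**What the plan says.** Section 2.1, Hypothesis I: "Lower MV measurements (corrected for total morphine equivalents administered) are correlated with lower TOF ratios". The opioid correction is part of the hypothesis.

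Section 2.7 B, item f: "We will use Pearson correlations and linear regressions, without regard to treatment group to compare". Four pairs follow. The first is "MV measurements and TOF ratios" and the second is "MV measurements and total opioid dose". The other two are pain with opioid dose and MV with pain. No covariate is named for any of them.

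The only multi-factor analysis is item e of the same section. Its factors are demographics and its stated purpose is to show that the groups are alike; neither opioid dose nor TOF ratio is named.

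Opioids also appear in items a.iii to a.vi (sustained low MV compared between arms, separately in patients with and without PACU opioids) and in item b.v (total PACU opioid dose by arm).

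Section 2.7 C tests the remaining secondary hypotheses, which include Hypothesis I, only if A1 and A2 are both significant.

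**The concern.** If item f is followed as written, the result offered for Hypothesis I will be an uncorrected correlation between MV and TOF ratio, which answers a different question. Opioids depress MV on the protocol's own premise: the legend to Figure 1 in section 2.2 describes a distinct fall in MV within 15 minutes of the first PACU opioid dose. If patients with lower TOF ratios also tend to have received more opioid, or less, part of the MV–TOF correlation belongs to the opioid. Depending on the direction of that link, the simple correlation can suggest an effect of residual block that is absent, or hide one that is present.

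The phrase linear regressions leaves room for covariates. As none is named, whether and how to correct for opioids would be decided after the data are seen.

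**Working it through.** **Text check.** Taking each analysis in section 2.7 B that involves at least two of the three variables, or that uses several factors:

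| Item | MV | TOF ratio | Opioid |
|---|---|---|---|
| a.iii–vi (by arm) | yes | no | PACU receipt, yes/no |
| e | yes | no | no |
| f.i | yes | yes | no |
| f.ii | yes | no | dose |

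No row has all three. Item b.v (dose by arm) and item f.iii (pain with dose) involve neither MV nor TOF.

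**Size of the possible bias.** The plan states no figure to reproduce here and gives no correlations, so what follows is an illustration on assumed inputs. Write M for MV, T for TOF ratio and O for opioid dose. The uncorrected correlation is

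r(M,T) = r_partial × √[(1 − r(M,O)²)(1 − r(T,O)²)] + r(M,O) × r(T,O).

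If TOF has no effect once opioids are allowed for (r_partial = 0), only the product r(M,O) × r(T,O) is left.

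Inputs: n = 300 (section 2.7 D). Assumed: an opioid effect of −8 points of % predicted MV per SD of dose, and a residual SD of 25 points. Then

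|r(M,O)| = 8 / √(8² + 25²) = 8 / √689 = 0.305.

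The chance of a two-sided p < 0.05 by Fisher's z, with z = atanh(r) × √297, is Φ(z − 1.96) + Φ(−z − 1.96):

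| Size of r(T,O), assumed | Spurious size of r(M,T) | z | Chance of significance |
|---|---|---|---|
| 0 | 0 | 0 | 5% |
| 0.1 | 0.030 | 0.53 | 8% |
| 0.2 | 0.061 | 1.05 | 18% |
| 0.3 | 0.091 | 1.58 | 35% |

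A stronger opioid effect enlarges the bias. With r(M,O) = −0.4 and r(T,O) = −0.3 the spurious r(M,T) is 0.12 and is significant in 55% of trials; with −0.6 and −0.3 it is 0.18 and 88%.

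**The bias can also mask an effect.** Take a true partial correlation of 0.20, r(M,O) = −0.6 and r(T,O) = +0.3. Then r(M,T) = 0.20 × √(0.64 × 0.91) − 0.18 = 0.153 − 0.18 = −0.03.

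**With no opioid–TOF correlation there is only attenuation.** For r_partial = 0.20 and r(M,O) = −0.4, r(M,T) = 0.20 × √0.84 = 0.18.

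**What an arm term would cost.** Keep the inputs above and assume a true slope of 4 points per 0.1 of TOF ratio, a TOF SD of 0.084 (so 3.36 points per SD), no opioid–TOF correlation, and arm explaining 21% of TOF variance. Power is approximately Φ(δ − 1.96):

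- TOF alone: δ = (3.36 / 26.25) × √300 = 2.22, power 60%.
- TOF and opioid dose: δ = (3.36 / 25) × √300 = 2.33, power 64%.
- TOF, opioid dose and arm: δ = 2.33 × √0.79 = 2.07, power 54%.

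The opioid term gains about 4 points of power here and the arm term loses about 10. If arm explained 40% of TOF variance, δ = 2.33 × √0.60 = 1.80 and power would be 44%.

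**The case against.** The strongest reply is that the plan already deals with opioids in several places, and much of it stands.

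- **Opioids are not ignored.** A reader might infer that they are, but item f.ii relates MV to opioid dose, item f.iii relates dose to pain, and item b.v compares dose by arm.
- **The two effects are not beyond separation.** Items a.iii to a.vi compare sustained low MV between arms "after opioid administration (amongst patients receiving opioids in the PACU" and "in the absence of opioids (amongst patients w/o opioids in the PACU". An arm difference among patients without PACU opioids is some evidence on residual block. It is limited: opioid receipt is determined after randomization, the split is yes or no, opioids given in the OR are not covered, and TOF is not used. It does not test Hypothesis I.
- **Secondary objective (b) does not ask for opioid-corrected MV.** A reader might infer this because it asks whether depression "is due to opioid administration vs. postoperative residual neuromuscular block". But the objective names its own method, a comparison of VAS scores and total opioid, and items b.iv, b.v and f.ii to f.iv supply it.
- **Pooling the arms is not in itself an error.** Hypothesis I asks for no arm adjustment. Arm is the randomized source of variation in TOF, and conditioning on it turns the question into a within-arm association.
- **The opioid–TOF link may be weak.** Care staff are blinded to the TOF values and to the numerical MV data (section 2.5), so they cannot dose opioids on those readings. Indirect links remain possible.
- **The stakes are limited**, because Hypothesis I is reached only after A1 and A2.

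None of this supplies an analysis with MV, TOF ratio and opioid dose together.

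**Conclusion.** The concern holds for Hypothesis I and goes no further. The hypothesis specifies an opioid-corrected association, and item f.i as written specifies an uncorrected one. That mismatch follows from the text and needs no assumption.

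The consequence is less certain. With an opioid effect of −8 points per SD, a residual SD of 25 and n = 300, the false-positive rate for a TOF effect runs from 5% to about 35% as the opioid–TOF correlation goes from 0 to 0.3. The documents do not show where in that range, or beyond it, the trial would lie. The documents do not support reading this as a failure of objective (b) or as a fault in pooling the arms. The primary and key secondary conclusions are untouched. It should be corrected because the repair is simple and makes the analysis match the hypothesis.

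**What to change.** In section 2.7 B, item f.i, state that Hypothesis I is tested by the TOF coefficient in a linear regression of % predicted MV on TOF ratio and cumulative morphine equivalents together, or by the equivalent partial correlation.

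Define matching time windows: MV averaged over a stated interval, the TOF ratio measured in or next to it, and opioid dose accumulated up to that interval. A whole-stay PACU total would count doses given after the MV reading. Section 2.5 continues TOF monitoring only until full recovery is documented, so the SAP should also say how patients without a later TOF value are handled.

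Keep the four simple correlations as descriptive. Add treatment arm and site only in a sensitivity analysis.

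The cost is SAP wording and slightly more analysis work. Section 2.5 already records MV, TOF, and the doses and times of all medications across the perioperative period, so no new data and no change in sample size or patient care are needed.
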